**[If no, thank the person for their time and end the interview.]**

This interview will be recorded, and then it will be transcribed with all personally identifying information removed. For research purposes only, other Cerner Enviza team members may listen in to this interview or they may listen to the recording. Do I have your permission to record the interview?

**[If no, thank the person for their time and end the interview.]**

Thank you! This is <*interviewer name*> interviewing <*Patient ID*> for <*Study ID*> at <*Current Time*> on <*Date of Interview*>.

Do you have any questions before we begin?

Proprietary and Confidential | Page 3

Participant Interview Guide CAB+RPV switch study

Participant ID Number: \_\_\_\_\_ Date of Interview: (month/day/year) \_\_\_\_\_ Interviewer Initials: \_\_\_\_\_

### Interview Guide

#### Ice-breaker questions

1. First, let's start by telling me a little bit about yourself, such as your age, who you live with, and your work.
2. What do you like to do in your free time?

#### Discussion theme 1. Perspectives on HIV treatment overall

3. Please take a look at the images below. Which image do you think best matches how you feel about HIV treatment in general?

- a. How did you come up with that image?
- b. How does HIV treatment fit into your life?

4. What would your ideal HIV treatment look like?

- a. How would it be administered?
- b. How frequently would it be taken?

5. What are your thoughts about Biktarvy compared to Cabenuva?

- a. Does one have advantages over the other in any way?
- b. Do they differ in how they make you feel about your HIV?

Participant Interview Guide CAB+RPV switch study

Participant ID Number: \_\_\_\_\_ Date of Interview: (month/day/year) \_\_\_\_\_ Interviewer Initials: \_\_\_\_\_

**Discussion theme 2. Initiating Cabenuva treatment**

I would like for you to think back to the time when you decided to start taking Cabenuva. I'm going to ask a few questions about your understanding of Cabenuva and what led you to begin with this treatment.

**6. How did you learn about Cabenuva?**

- a. *How did you hear about Cabenuva?*
  - i. *Who did you first hear about it from?*
- b. *How was the treatment explained to you?*

**7. What factors contributed to your decision to start Cabenuva?**

- a. *Were you taking HIV treatment before starting Cabenuva?*
  - i. *What factors led you to switch to Cabenuva from your previous medication?*
- b. *What information did you use to make your decision to start Cabenuva?*
- c. *Who did you talk with to help make your decision?*
- d. *To what extent was your healthcare provider involved in your decision to start Cabenuva?*

**8. What expectations did you have of Cabenuva prior to starting?**

- a. *Thinking back to before you started receiving Cabenuva, do you feel that you were provided adequate information about the treatment?*
- b. *Did you have any concerns before taking Cabenuva?*  
*What did your provider do to address your concerns?*
- c. *Is there any information that you wish you had known before starting Cabenuva?*
  - i. *Did you feel prepared for...*
    - 1. *what the injections might feel like?*
    - 2. *frequency of visits to receive injections?*
    - 3. *side-effects/injection site reactions?*

Proprietary and Confidential | Page 5

Participant Interview Guide CAB+RPV switch study

Participant ID Number: \_\_\_\_\_ Date of Interview: (month/day/year) \_\_\_\_\_ Interviewer Initials: \_\_\_\_\_

**Discussion theme 3. Cabenuva Treatment Experience and Perceptions**

9. When did you start taking Cabenuva? For how long did you take Cabenuva?
10. What feelings did you have starting treatment with Cabenuva?
11. What was your initial experience at the clinic when starting Cabenuva?
  - a. Was there anything that you found helpful at your first visits? Was there anything that you found unhelpful at your first visits?
  - b. How were your interactions with the provider and other staff?
12. How many different times did you receive Cabenuva injections?
13. What was your experience like receiving the Cabenuva injections?
  - a. How did the injections make you feel at first?
  - b. How did you feel after the injections?
    - i. Did you experience any issues with the injections?
  - c. Did you ever miss a Cabenuva injection appointment because you did not want the injection? For any other reasons?
  - d. How did your experience change after your first dose or few doses (injections)?
    - i. Were there any changes that made these injections easier? Any changes that made these injections more difficult?
14. Overall, how did you feel about your treatment with Cabenuva?
  - a. What did you like about Cabenuva?
  - b. What didn't you like about it?
15. How does Cabenuva compare to other HIV treatments that you've received before Cabenuva?
  - a. To what extent were you comfortable with the way Cabenuva treatment is given? How about the 2-month schedule?
  - b. Did taking Cabenuva affect your quality of life? In what ways?
  - c. To what extent did treatment with Cabenuva impact your outlook for the future?
16. What led you to decide to stop your treatment with Cabenuva?
  - a. Is there anything that would have made you stay on Cabenuva?

Participant Interview Guide CAB+RPV switch study

Participant ID Number: \_\_\_\_\_ Date of Interview: (month/day/year) \_\_\_\_\_ Interviewer Initials: \_\_\_\_\_

**Discussion theme 4. Biktarvy Treatment Experience and Perceptions**

17. Now let's talk about your decision to switch to Biktarvy. How did you learn about Biktarvy?
  - a. How did you hear about Biktarvy?
    - i. Who did you first hear about it from?
  - b. How was the treatment explained to you?
18. What factors contributed to your decision to start (or re-start) Biktarvy?
  - a. What factors led you to switch to Biktarvy?
  - b. What information did you use to make your decision?
  - c. Who did you talk with to help make your decision?
  - d. To what extent was your healthcare provider involved in your decision to start Biktarvy?
19. What expectations did you have of Biktarvy prior to starting?
  - a. Thinking back to before you switched to Biktarvy, do you feel that you were provided adequate information about the treatment?
  - b. Did you have any concerns before taking Biktarvy?
    - i. What did your provider do to address your concerns?
  - c. Is there any information that you wish you had known before starting Biktarvy?
20. Prior to starting Biktarvy following switching from Cabenuva, had you ever taken Biktarvy before?
21. What feelings have you had since starting (or re-starting) treatment with Biktarvy?
  - a. How does it feel to take Biktarvy?
    - i. Do you experience any issues taking Biktarvy?
  - b. How has your experience changed after your few doses?
    - i. Were there any changes that made taking Biktarvy easier? Any changes that made taking Biktarvy more difficult?
22. Overall, how do you feel about your treatment with Biktarvy?
  - a. Is there anything you like about taking Biktarvy?
23. How does Biktarvy compare to other HIV treatments you've received?
  - a. To what extent are you comfortable with the way Biktarvy treatment is given?
  - b. Does treatment with Biktarvy affect your quality of life? In what ways?
  - c. How does treatment with Biktarvy impact your outlook for the future?
24. Do you ever miss taking any doses of your HIV therapy on time? If yes, how often? Why?
  - a. What helps you to take Biktarvy on time?

Proprietary and Confidential | Page 7

Participant Interview Guide CAB+RPV switch study

Participant ID Number: \_\_\_\_\_ Date of Interview: (month/day/year) \_\_\_\_\_ Interviewer Initials: \_\_\_\_\_

25. So, we are coming to the end of our discussion. Is there anything else that you would like to share about your experience you're your HIV treatment experiences?

□□

*We are finished with the interview. Thank you very much for taking the time to speak with me today.*

Proprietary and Confidential | Page 8

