The objective of this study is to evaluate safety, pharmacokinetic(s) (PK), and efficacy during the extended CAB pharmacologic decline, which will inform clinical decisions for PWH who elect or require discontinuation of CAB+RPV. Additionally, qualitative and quantitative participant-reported data will help determine the net benefit of switching off an injectable requiring Q2 monthly visits. Ultimately, study data will assess if B/F/TAF is a safe and effective option after CAB+RPV discontinuation. Retrospective cohort data could answer some of the questions, but would take time to accumulate and would not provide PRO or nuanced pharmacokinetic, tolerability, and toxicity data.

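### The interview guide prompts for likes and dislikes of Cabenuva but, in the matching question, only for likes of Biktarvy: a minor risk of one-directional prompting in an exploratory endpoint

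*Protocol*

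**What the plan says.** Protocol Section 2 lists participants' experience with CAB+RPV and their preferences between injectable and oral therapy as an exploratory endpoint. Section 1.3 says that qualitative and quantitative "participant-reported data will help determine the net benefit of switching off an injectable requiring Q2 monthly visits". The interview guide in Appendix 11.4.2 (version 1.0) takes Cabenuva in themes 2 and 3 and Biktarvy in theme 4.

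- **Overall view.** Q14 on Cabenuva carries two probes, "What did you like about Cabenuva" (14a) and "What didn't you like about it" (14b). Q22 on Biktarvy carries one, "Is there anything you like about taking Biktarvy" (22a).
- **Information wished for beforehand.** Q8c on Cabenuva has a sub-probe on feeling prepared. It covers the feel of the injections, visit frequency and "side-effects/injection site reactions". Q19c on Biktarvy has the same stem and no sub-probe.
- **Problems during treatment.** These are asked for both drugs: "Did you experience any issues with the injections" (13b.i) and "Do you experience any issues taking Biktarvy" (21a.i).

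The guide's instructions say that it is not to be followed word for word and allow unscripted probes.

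**The concern.** When two treatments are explored with one template, a probe present for one and absent for the other shapes what participants volunteer. Here both gaps fall on the same side. The interviewer is cued to ask what was disliked about the injectable and whether participants were ready for its side effects, and gets no such cue for the sponsor's tablet. The guide's own aim includes experience after the switch and preference between the two forms of therapy, and Section 1.3 ties these data to the net benefit of switching. A report that set negative themes for the two drugs side by side would partly reflect what was asked.

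**Working it through.** The plan gives no figure to reproduce, so the check is an item-by-item comparison of the Cabenuva questions (Q6 to Q16) with the Biktarvy questions (Q17 to Q24).

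**Step 1: like and dislike probes.**

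| | Like | Dislike |
|---|---|---|
| Cabenuva (Q14) | 1 (14a) | 1 (14b) |
| Biktarvy (Q22) | 1 (22a) | 0 |

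No question elsewhere in the guide asks directly what participants dislike about Biktarvy.

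**Step 2: other prompts that invite negative content.** Classifying them takes some judgement.

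| Topic | Cabenuva | Biktarvy |
|---|---|---|
| Concerns beforehand | 8b | 19b |
| Issues | 13b.i | 21a.i |
| Changes that made it harder | 13d.i | 21b.i |
| Missed appointments or doses | 13c | 24 |
| Prepared for side effects | 8c.i.3 | none |
| Anything unhelpful at first visits | 11a | none |
| Dislikes | 14b | none |
| Why treatment was stopped | 16 | none |

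The totals are 8 for Cabenuva and 4 for Biktarvy. Four pairs match, and the 8 − 4 = 4 unmatched prompts are all on the Cabenuva side.

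**Step 3: which unmatched prompts matter.** Q16 is unmatched by design, because every participant is leaving Cabenuva. Q11a concerns the first injection visits. The first two items of 8c.i concern injections and injection visits and have no direct tablet equivalent. The dislike probe (14b) and the side-effect item (8c.i.3) are not specific to injections and could have been mirrored. The avoidable asymmetry is therefore two probes.

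**Step 4: side effects by name.** Theme 4 does not mention them. Theme 3, the Cabenuva experience section, does not either. The single mention, in Q8c, is about preparedness. Prompts by name at the experience stage are therefore 0 for Cabenuva and 0 for Biktarvy.

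**Step 5: number affected.** About 35 participants are planned, of whom about 10 in France are not interviewed: 35 − 10 = 25. This is a ceiling, because Protocol Section 6.5.1.4 limits interviews to English and to those who consent.

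**The case against.** The strongest reply is that Biktarvy negatives are not shut out. Q21 asks about issues and also "Any changes that made taking Biktarvy more difficult", Q19b asks about concerns, and Q24 asks about missed doses. Q5 is a neutral head-to-head question, the stem of Q22 is open, and Q25 is an open close. Nor does all the wording lean one way: 14a presupposes that something was liked about Cabenuva, whereas 22a does not presuppose it for Biktarvy, and 16a asks what would have kept participants on Cabenuva. Outside the interview, the Week 4 study questionnaire (Appendix 11.4.3) asks about Biktarvy side effects, whether they persist, their effect on daily activities and how much they bother the participant. The HIVTSQ has items on side effects and on pain or discomfort.

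Most of this stands, and it rules out stronger readings that a reader might infer:

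- *That the guide asks only for positives about Biktarvy, or is parallel except where negatives would arise.* The four matched pairs contradict both.
- *That Biktarvy side effects go uncollected.* The questionnaires collect them, and Section 6.5.1.4 requires interviewers to pass on adverse events that come up.
- *That a planned comparison of theme counts is invalid.* No such comparison is planned. Protocol Section 8.8.1 says only that these experiences may be explored, and SAP Section 9.2 specifies no method for comparing interview themes.
- *That the instrument is shown to favour the sponsor's product.* The wording shows a risk; nothing in the documents shows a resulting bias.

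The reply does not remove the gap. Each Biktarvy negative prompt has a Cabenuva counterpart, so none stands in for the missing probe. The unscripted probes listed in the guide are for clarifying and extending answers, and none raises dislikes. Questionnaire data do not balance the open-ended interview material.

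**Conclusion.** The asymmetry is real and minor. Two probes that could have been mirrored, one on dislikes and one on preparedness including side effects, are present for Cabenuva and absent for Biktarvy. They affect an exploratory endpoint in at most about 25 interviews and touch no primary or secondary endpoint. The consequence is a risk of one-directional prompting, which would matter mainly if negative themes were compared between the drugs in a report or publication.

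This rests on two assumptions: that interviewers broadly follow the printed probes, and that the guide in the protocol is the one used. SAP Section 1.2.1 describes the interviews in the past tense and Section 2.1.1 does the same for the North American Week 12 interim analysis. Many or all interviews may therefore already be complete, in which case only the reporting remedy remains.

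**What to change.** For any interviews still to come, or if the guide is reused:

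- Add 22b: *Is there anything you don't like about taking Biktarvy?*
- Add a sub-probe under 19c, such as: *Did you feel prepared for taking a tablet every day / side effects?*

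The cost is a new guide version with the ethics notification that it needs, and about two minutes of the 60-minute interview.

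For interviews already held with version 1.0, state the difference in prompting wherever the results are reported, and do not compare the frequency of negative themes between the two drugs. One sentence to this effect in SAP Section 9.2 would be enough, at almost no cost.

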#### **11.4.3. Study GS-US-380-6730 Additional Study Specific Questions for Participant**

Day 1 additional study specific questions begins on the following page.

Participant ID Number: \_\_\_\_\_ Date of Survey: (month/day/year) \_\_\_\_\_

**GS-US-380-6738: A Phase 4 Study to Evaluate the Safety, Pharmacokinetics and of Oral  
B/F/TAF after Discontinuing Injectable CAB + RPV**

Thank you for taking our survey. The goal of this survey to better understand your experience with your current (CAB + RPV) and new (B/F/TAF) HIV treatments.

The questions below will ask you to select **only one** option from the list **or select all that apply**. Some questions may also ask for you to include additional details in the space provided. Please read each question carefully and mark with an "X" the option(s) that best apply to you. Please answer all questions on each page of the survey, unless you are instructed to skip questions based on your answers.

**EXAMPLE:**

What is your favorite fruit to eat?

Apple	
Banana	
Blueberry	
Orange	
Raspberry	
Strawberry	
Some other fruit	
I do not like to eat fruit	

Participant ID Number: \_\_\_\_\_ Date of Survey: (month/day/year) \_\_\_\_\_

**Day 1: Questions related to participant experience with CAB + RPV (Cabenuva)**

**1. How did you first hear about injectable CAB + RPV (Cabenuva)?**

*Please check the  
one best answer*

From a doctor, nurse, social worker or other healthcare provider	 (a)
From a friend, relative, partner, acquaintance or other patient	 (b)
From an advertisement (TV, radio, internet, magazine, etc.)	 (c)
Internet (search, social media, etc.)	 (d)
Another source ( please describe in the box below )	 (y)
Don't remember	 (z)

→ **DESCRIBE BELOW**

*If you selected "Another source", please describe that here:*

Participant ID Number: \_\_\_\_\_ Date of Survey: (month/day/year) \_\_\_\_\_

**2. Which of the following factors led you to decide to take injectable CAB + RPV (Cabenuva)?**

*Please check all answers that apply*

A friend, relative, partner, acquaintance or other patient recommended it	 (a)
A doctor, nurse, social worker or other health practitioner	 (b)
Research I did on my own (such as internet searches)	 (c)
Advertisement (TV, radio, internet, magazine, etc.)	 (d)
Wanting to reduce or stop side effects from daily oral medication	 (e)
Fear of stigma or negative feelings from taking HIV medication every day	 (f)
Fear that others will be more likely to know I have HIV with daily oral medication	 (g)
Not needing to remember to take daily oral medication	 (h)
Fear of missing doses of daily oral HIV medications	 (i)
Wanting to forget about having HIV for a while (no reminder every day)	 (j)
More convenient than oral treatment	 (k)
I think injections would work better than daily oral medication	 (l)
It is a new and exciting HIV treatment	 (m)
Want to have more in-person contact with healthcare system	 (n)
Another reason (please describe in the box below)	 (y)

→ DESCRIBE BELOW

*If you selected "Another reason", please describe that here:*

Participant ID Number: \_\_\_\_\_ Date of Survey: (month/day/year) \_\_\_\_\_

3. Of the reasons you checked in question number 2 above, which would you rank as the TOP reason you started injectable CAB + RPV (Cabenuva)?

*Please check the  
one best answer*

A friend, relative, partner, acquaintance or other patient recommended it	 (a)
A doctor, nurse, social worker or other health practitioner	 (b)
Research I did on my own (such as internet searches)	 (c)
Advertisement (TV, radio, internet, magazine, etc.)	 (d)
Wanting to reduce or stop side effects from daily oral medication	 (e)
Fear of stigma or negative feelings from taking HIV medication every day	 (f)
Fear that others will be more likely to know I have HIV with daily oral medication	 (g)
Not needing to remember to take daily oral medication	 (h)
Fear of missing doses of daily oral HIV medications	 (i)
Wanting to forget about having HIV for a while (no reminder every day)	 (j)
More convenient than oral treatment	 (k)
I think injections would work better than daily oral medication	 (l)
It is a new and exciting HIV treatment	 (m)
Want to have more in-person contact with healthcare system	 (n)
Other reason ( described in the box below Question 2 )	 (y)

4. During your time taking CAB + RPV (Cabenuva), how inconvenient was it to go to the clinic/doctor's office to receive CAB + RPV (Cabenuva) injections as directed?

*Please check the  
one best answer*

Not at all inconvenient	 (a)
A little inconvenient	 (b)
Moderately inconvenient	 (c)
Very inconvenient	 (d)
Extremely inconvenient	 (e)

Participant ID Number: \_\_\_\_\_ Date of Survey: (month/day/year) \_\_\_\_\_

5. Did you reschedule any appointments for getting your CAB + RPV (**Cabenuva**) injections in the past 6 months?

*Please check the one best answer.*

I did not reschedule any appointments	 (a)
I rescheduled 1-2 appointments	 (b)
I rescheduled 3-4 appointments	 (c)
I rescheduled 5 or more appointments	 (d)

6. Did you miss any appointments entirely for getting your CAB + RPV (**Cabenuva**) injections in the past 6 months?

*Please check the one best answer.*

I did not miss any appointments	 (a)
Missed 1-2 appointments	 (b)
Missed 3-4 appointments	 (c)
Missed 5 or more appointments	 (d)

*Skip to Question 8*

Participant ID Number: \_\_\_\_\_ Date of Survey: (month/day/year) \_\_\_\_\_

7. Did missing appointments in the last 6 months lead to receiving CAB + RPV (**Cabenuva**) injections late or outside of the window when you were supposed to receive them?

Please check the one best answer.	
Yes	 (a)
No	 (b)
I don't know	 (c)

8. Which of the following side effects did you experience while on CAB + RPV (**Cabenuva**)?

Please check all answers that apply	
Pain from the injection	 (a)
Soreness from the injection	 (b)
Lump, bump or nodule from the injection	 (c)
Swelling around the injection site	 (d)
Redness around injection site	 (e)
Itching at the injection site	 (f)
Muscle aches	 (g)
Headache	 (h)
Nausea / Upset stomach	 (i)
Diarrhea	 (j)
Sleep problems	 (k)
Dizziness	 (l)
Allergic reaction (rash, fever, blisters, tiredness, trouble breathing)	 (m)
Fatigue / Tiredness	 (n)
Another side effect (please describe in the box below)	 (y)
I did not experience any side effects while on CAB + RPV (Cabenuva)	 (z)

→ DESCRIBE BELOW

→ SKIP TO QUESTION 11

If you selected "Another side effect", please describe that here:

Participant ID Number: \_\_\_\_\_ Date of Survey: (month/day/year) \_\_\_\_\_

**9. Did you experience any side effects that affected your ability to do your daily activities?**

	Please check the one best answer.
Yes	 (a)
No	 (b)

**10. How much did the side effects experienced while on CAB + RPV (Cabenuva) bother you?**

	Please check the one best answer
They don't bother me at all	 (a)
I am a little bothered by them	 (b)
I am moderately bothered by them	 (c)
I am very bothered by them	 (d)
I am extremely bothered by them	 (e)

Participant ID Number: \_\_\_\_\_ Date of Survey: (month/day/year) \_\_\_\_\_

11. Why did you decide to switch from CAB + RPV (Cabenuva) to daily oral medication B/F/TAF (Biktarvy)?

*Please check all answers that apply*

I didn't like the side effects of CAB + RPV (Cabenuva)	 (a)
Visits to the clinic were too frequent	 (b)
Waiting time in the office to get injections	 (c)
Difficulty with insurance or cost	 (d)
Difficulty scheduling appointments for injections	 (e)
I want to have less in-person contact with the healthcare system	 (f)
I have anxiety about receiving injections	 (g)
I prefer oral medication over injections	 (h)
A doctor, nurse, social worker or other health practitioner said I should switch	 (i)
A friend, relative, partner, acquaintance or other patient said I should switch	 (j)
I already take on other daily oral medication, so taking one more wouldn't make a difference	 (k)
Concern that the medication in the injection might not last 2 months	 (l)
Concern about developing resistance with CAB + RPV (Cabenuva)	 (m)
I want to be in more control of my HIV medication	 (n)
I took B/F/TAF (Biktarvy) before and I had a good experience with it	 (o)
I think B/F/TAF (Biktarvy) is more effective than CAB + RPV (Cabenuva)	 (p)
I think B/F/TAF (Biktarvy) has less side effects than CAB + RPV (Cabenuva)	 (q)
Another reason (please describe in the box below)	 (y)

→ DESCRIBE BELOW

*If you selected "Another reason", please describe that here:*

Participant ID Number: \_\_\_\_\_ Date of Survey: (month/day/year) \_\_\_\_\_

12. Of all the reasons you checked in question 10, which would you rank as the TOP reason you decided to switch from CAB + RPV (**Cabenuva**) to daily oral medication B/F/TAF (Biktarvy)?

*Please check the  
one best answer*

I didn't like the side effects	 (a)
Visits to the clinic were too frequent	 (b)
Waiting time in the office to get injections	 (c)
Difficulty with insurance or cost	 (d)
Difficulty scheduling appointments for injections	 (e)
I want to have less in-person contact with the healthcare system	 (f)
I have anxiety about receiving injections	 (g)
I prefer oral medication over injections	 (h)
A doctor, nurse, social worker or other health practitioner said I should switch	 (i)
A friend, relative, partner, acquaintance or other patient said I should switch	 (j)
I already take on other daily oral medication, so taking one more wouldn't make a difference	 (k)
Concern that the medication in the injection might not last 2 months	 (l)
Concern about developing resistance with CAB + RPV (Cabenuva)	 (m)
I want to be in more control of my HIV medication	 (n)
I took B/F/TAF (Biktarvy) before and I had a good experience with it	 (o)
I think B/F/TAF (Biktarvy) is more effective than CAB + RPV (Cabenuva)	 (p)
I think B/F/TAF (Biktarvy) has less side effects than CAB + RPV (Cabenuva)	 (q)
Another reason ( described in the box below Question 10 )	 (y)

13. How hopeful do you feel about starting Biktarvy in terms of successfully treating your HIV?

*Please check the  
one best answer*

Very hopeful	 (a)
Hopeful	 (b)
Somewhat hopeful	 (c)

Participant ID Number: \_\_\_\_\_ Date of Survey: (month/day/year) \_\_\_\_\_

Not hopeful at all	 (d)
--------------------	---------------------------

